4.15.7 Physical Examination

Data will not be summarized or listed.

4.15.8 Tissue/Blood Samples for Biomarkers

Data will not be summarized or listed.

5 INTERIM ANALYSIS

No formal pre-specified interim analyses are planned as this is a single arm, open-label, phase 1/2 study, however data may be summarized periodically throughout the study based on a separate plan(s).

6 DATA SAFETY MONITORING BOARD ANALYSIS

No data safety monitoring board (DSMB) analyses are planned.

7 CHANGES TO PLANNED PROTOCOL ANALYSIS

Due to the termination of this study, the scope of reporting has changed. This amendment documents the analyses to be performed, which are generally consistent with the protocol, but reflects the reduction in the scope of reporting.

QMD Ref: CCI	Governing QMD: CCI
Confidentiality Statement	
CCI	

	CCI		
	CCI	Sponsor:	Theseus Pharmaceuticals, Inc.
		Protocol Number:	THE630-21-101
STATISTICAL ANALYSIS PLAN. PHASE 2-3-4			

9 LIST OF TABLES, FIGURES AND LISTINGS

The following table includes details of the tables, figures and listings to be included within each section of the eCTD. The eCTD section is shown in bold. The following validation methods maybe used:

- Independent programming of numbers and manual review of format (IP)
- Independent programming by statistician of numbers and manual review of format (Stat IP)
- Manual review (MR)
- Code review (CR)

Phase 1 (Dose escalation (DE)) versions of displays will be created. Please note that in titles where text “<phase>” appears, this text should be replaced with “(Phase 1)”.

Table Number	Table Title	Validation Method	Shell Number (if repeat)
Items in bold are not table titles but references to the section headings within eCTD.			
14.1	Demographics Data		
14.1.1	Disposition		
14.1.1.1 DE	Analysis Sets – Screened Set <Phase>	IP	
14.1.1.2 DE	Screen Failures – Screened Set <Phase>	IP	
14.1.1.3 DE	Inclusion/Exclusion Violations– Screened Set <Phase>	IP	
14.1.1.4 DE	Discontinuation – Full Analysis Set <Phase>	IP	
14.1.1.5 DE	Duration of Follow-Up (months)– Full Analysis Set <Phase>	IP	
14.1.1.6 DE	Major Deviations-Full Analysis Set <Phase>	IP	
14.1.2	Demographics		

QMD Ref: CCI	Governing QMD: CCI
Confidentiality Statement	
CCI	

CCI		Sponsor: Theseus Pharmaceuticals, Inc.	
CCI		Protocol Number: THE630-21-101	
STATISTICAL ANALYSIS PLAN. PHASE 2-3-4			

Table Number	Table Title	Validation Method	Shell Number (if repeat)
14.1.2 DE	Demographics – Full Analysis Set <Phase>	IP	
14.1.3	Baseline Characteristics		
14.1.3.1 DE	Medical or Surgical History – Full Analysis Set <Phase>	IP	
14.1.3.2 DE	Reported Mutation Status History- Full Analysis Set <Phase>	IP	
14.1.3.3 DE	Baseline Characteristics -Full Analysis Set <Phase>	IP	
14.1.3.4 DE	Prior Systemic Anticancer Therapy Related to GIST-Full Analysis Set <Phase>	IP	
14.2	Efficacy Data		
14.2.1	Primary Efficacy Endpoint		
14.2.1.1 DE	Confirmed ORR, BOR and Time to Response-Full Analysis Set <Phase>	Stat IP/IP	
14.2.2	Secondary Efficacy Endpoints		
14.2.2.1 DE	DCR and CBR-Full Analysis Set <Phase>	Stat IP/IP	
14.2.3	Exploratory Endpoints		
14.3	Safety Data		
14.3.1	Displays of Adverse Events		
14.3.1.1 DE	Adverse Events, Overall Summary of Treatment-Emergent Adverse Events (TEAEs) – Full Analysis Set <Phase>	IP	
14.3.1.2 DE	Adverse Events, TEAEs by System Organ Class and Preferred Term – Full Analysis Set <Phase>	IP	
14.3.1.3 DE	Adverse Events, TEAEs ≥ Grade 3 by System Organ Class and Preferred Term – Full Analysis Set <Phase>	IP	14.3.1.2
14.3.1.4 DE	Adverse Events, Treatment-Related TEAEs by System Organ Class and Preferred Term – Full Analysis Set <Phase>	IP	14.3.1.2
14.3.1.5 DE	Adverse Events, Treatment-Related TEAEs ≥ Grade 3 by System Organ Class and Preferred Term – Full Analysis Set <Phase>	IP	14.3.1.2

QMD Ref: CCI	Governing QMD: CCI
Confidentiality Statement	
CCI	

CCI		Sponsor:		Theseus Pharmaceuticals, Inc.
CCI		Protocol Number:		THE630-21-101
STATISTICAL ANALYSIS PLAN. PHASE 2-3-4				

Table Number	Table Title	Validation Method	Shell Number (if repeat)
14.3.1.6 DE	Adverse Events, Serious TEAEs by System Organ Class and Preferred Term –Full Analysis Set <Phase>	IP	14.3.1.2
14.3.1.7 DE	Adverse Events, Serious Treatment-Related TEAEs by System Organ Class and Preferred Term – Full Analysis Set <Phase>	IP	14.3.1.2
14.3.1.8 DE	Adverse Events, TEAEs Leading to Discontinuation of Study Drug by System Organ Class and Preferred Term-Full Analysis Set <Phase>	IP	14.3.1.2
14.3.1.9 DE	Adverse Events, TEAEs Leading to Interruptions of Study Drug by System Organ Class and Preferred Term-Full Analysis Set <Phase>	IP	14.3.1.2
14.3.1.10 DE	Adverse Events, TEAEs Leading to Dose Reductions of Study Drug by System Organ Class and Preferred Term-Full Analysis Set <Phase>	IP	14.3.1.2
14.3.1.11 DE	Adverse Events, TEAEs by System Organ Class, Preferred Term, and Maximum Toxicity-Full Analysis Set <Phase>	IP	
14.3.1.12 DE	Adverse Events, Treatment-related TEAEs by System Organ Class, Preferred Term, and Maximum Toxicity-Full Analysis Set <Phase>	IP	14.3.1.17
14.3.1.13 DE	Adverse Events, Fatal TEAEs by System Organ Class and Preferred Term- Full Analysis Set <Phase>	IP	14.3.1.2
14.3.1.14 DE	Adverse Events, Post-Treatment Treatment Related SAEs by System Organ Class and Preferred Term-Full Analysis Set <Phase>	IP	14.3.1.2
14.3.1.15 DE	Adverse Events, Dose Limiting Toxicities During Cycle 1 by Preferred Term and Maximum Toxicity- DLT Evaluable Analysis Set <Phase>	IP	14.3.1.2
14.3.2	Listings of Deaths, Other Serious and Significant Adverse Events		
14.3.2.1 DE	Fatal TEAEs, Listing – Full Analysis Set <Phase>	IP	
14.3.2.2 DE	All Deaths, Listing – Full Analysis Set <Phase>	IP	
14.3.2.3 DE	SAE, Listing – Full Analysis Set <Phase>	IP	

QMD Ref: CCI	Governing QMD: CCI
Confidentiality Statement	
CCI	

CCI		Sponsor: Theseus Pharmaceuticals, Inc.	
CCI		Protocol Number: THE630-21-101	
STATISTICAL ANALYSIS PLAN. PHASE 2-3-4			

Table Number	Table Title	Validation Method	Shell Number (if repeat)
14.3.2.4 DE	TEAEs Reported as Dose Limiting Toxicity, Listing – Full Analysis Set <Phase>	IP	
14.3.3	Narratives of Deaths, Other Serious and Certain Other Significant Adverse Events		
14.3.4	Abnormal Laboratory Values		
14.3.4.1 DE	Laboratory, Listing of Abnormal Values – Full Analysis Set <Phase>	IP	
14.3.4.2 DE	Hematology, CTCAE Grade Shifts from Baseline to Worst Post-Baseline Grade – Full Analysis Set <Phase>	IP	
14.3.4.3 DE	Chemistry, CTCAE Grade Shifts from Baseline to Worst Post-Baseline Grade – Full Analysis Set <Phase>	IP	14.3.4.2
14.3.4.4 DE	Coagulation, CTCAE Grade Shifts from Baseline to Worst Post-Baseline Grade – Full Analysis Set <Phase>	IP	14.3.4.2
14.3.4.5 DE	Potential Hepatotoxicity based on Hy’s law – Full Analysis Set <Phase>	IP	
14.3.4.6 DE	Laboratory, Listing of Patients with Potential Hepatotoxicity based on Hy’s law -Full Analysis Set <Phase>	IP	
14.3.5	Extent of Exposure, Dosage Information, And Compliance		
14.3.5.1 DE	Exposure to Study Drug- Full Analysis Set <Phase>	IP	
14.3.5.2 DE	Compliance to Study Drug During Cycle 1 -Full Analysis Set <Phase>	IP	
14.3.6	Vital Signs and Physical Examination		
14.3.6.1 DE	Vital Signs: Blood Pressure Shifts from Baseline to Maximum Post-baseline Value – Full Analysis Set <Phase>	IP	
14.3.7	Other Safety		
14.3.7.1 DE	Echocardiogram/MUGA, Descriptive Statistics-Full Analysis Set <Phase>	IP	
14.3.7.2 DE	ECG, QTcF values of Potential Clinical Concern Any Time, Post-baseline by Category-Full Analysis Set <Phase>	IP	
14.3.8	Concomitant Medication		
14.4	PK Tables		
QMD Ref: CCI		Governing QMD: CCI	
Confidentiality Statement			
CCI			

CCI		Sponsor: Theseus Pharmaceuticals, Inc.	
CCI		Protocol Number: THE630-21-101	
STATISTICAL ANALYSIS PLAN. PHASE 2-3-4			

Table Number	Table Title	Validation Method	Shell Number (if repeat)
14.5	PD Tables		
14.6	Other Data		

QMD Ref: CCI	Governing QMD: CCI
Confidentiality Statement	
CCI	

CCI			
CCI		Sponsor:	Theseus Pharmaceuticals, Inc.
		Protocol Number:	THE630-21-101
STATISTICAL ANALYSIS PLAN. PHASE 2-3-4			

Figure Number	Figure Title	Validation Method	Shell Number (if repeat)
14.2.1.3 DE	Best % Change from Baseline in Sum of the Longest Diameter of Target Lesion -Full Analysis Set <Phase>	IP	
14.2.1.4 DE	Swimmers Plot, Duration of treatment -Full Analysis Set <Phase>	IP	

QMD Ref: CCI	Governing QMD: CCI
Confidentiality Statement	
CCI	

CCI		Sponsor: Theseus Pharmaceuticals, Inc.	
CCI		Protocol Number: THE630-21-101	
STATISTICAL ANALYSIS PLAN. PHASE 2-3-4			

Listing Number	Listing Title	Validation Method	Shell Number (if repeat)
16.2	Patient Data Listings		
16.2.1	Discontinued Patients		
16.2.2	Protocol Deviations		
16.2.3	Patients Excluded from The Efficacy Analyses		
16.2.4	Demographic Data		
16.2.5	Compliance and / or Drug Concentration Data		
16.2.6	Individual Efficacy Response Data		
16.2.7	Adverse Event Listings		
16.2.8	Individual Laboratory Measurements and Other Safety		

QMD Ref: CCI	Governing QMD: CCI
Confidentiality Statement	
CCI	

CCI		Sponsor: Theseus Pharmaceuticals, Inc.	
CCI		Protocol Number: THE630-21-101	
STATISTICAL ANALYSIS PLAN. PHASE 2-3-4			

10 APPENDIX 1: RECIST

In this study, the overall RECIST response at a given time point (overall visit response) is determined by investigator based on RECIST 1.1 guidelines modified for GIST. It is based on investigator reported target lesion response, non-target lesion response and presence of any new lesions. For analysis purposes, overall visit response will be derived via programming based on

- deriving target lesion response (via programming),
- non-target lesion response (as collected)
- presence of new lesions (as collected).

10.1 Target Lesion Response

For purposes of analysis, target lesion response will be derived via programming.

Target lesion response is based on the sum of the longest diameters (SLD) of the target lesions.

Target Lesion Response	Criteria
Complete Response (CR)	Disappearance of all target lesions.
Partial Response (PR)	At least a 30% decrease in the SLD of target lesions from baseline (e.g., reference baseline SLD).
Progressive Disease (PD)	
 • At least a 20% increase in the SLD taking as reference the smallest SLD on the study (including baseline sum if that is the smallest on the study; reference referred to as nadir) • and SLD must also demonstrate an absolute increase of at least 0.5 cm from nadir (i.e., change from nadir in SLD ≥ 0.5cm). 
Or
 
 • Any re-appearance of one or more target lesions after an overall visit response (see 12.2) of complete response (CR) had been achieved at a prior visit.
Stable Disease (SD)	Neither sufficient shrinkage to qualify for PR nor sufficient increase to qualify for PD.

QMD Ref: CCI	Governing QMD: CCI
Confidentiality Statement	
CCI	

CCI		Sponsor:		Theseus Pharmaceuticals, Inc.
CCI		Protocol Number:		THE630-21-101
STATISTICAL ANALYSIS PLAN. PHASE 2-3-4				

Non-Evaluable (NE)	One or more lesions cannot be evaluated because of missing data or poor image quality unless a convincing argument can be made that the contribution of the individual missing lesion(s) would not change the assigned time point response (e.g., PD based on other findings).
--------------------	--

Sum of the longest diameter of target lesions

Target lesions (up to 5 lesions) are identified at baseline. The longest diameter (LD) of a target lesion is measured in cm. The sum of the longest diameter (SLD) of all target lesions measured at a given tumor assessment will be calculated by summing the measurements together. At post-baseline tumor assessments, the same target lesions identified at baseline should be assessed using the same method of scan. An indicator flag will be created to flag post-tumor assessments where one or more identified target lesions were not assessed or marked as not evaluable and thus the LD measurement is missing (e.g., MTLFLG=1 for yes). An indicator flag will also be created to flag post-tumor assessments where the scan method does not match baseline scan method.

For purposes of determining target lesion response, SLD, percent change from baseline, and percent change from nadir for post-baseline tumor assessments will be calculated regardless of missing target tumor LD measurements. That said SLD results from assessments with missing target lesion measurements will be excluded from other analyses (e.g., best percent change from baseline) if the derived target lesion response at said visit is NE. Change in method of scan of target lesions will not be taken into account when calculating SLD.

Percent change from baseline in SLD/Percent change from Nadir in SLD

The following calculations for post-baseline tumor assessments at a given visit will help with assigning target tumor response at given visit:

Percent change from baseline in SLD = (SLD at a given post-baseline visit – baseline SLD)/(baseline SLD) x 100.

Percent change from nadir in SLD = (SLD at a given post-baseline visit – nadir SLD)/(nadir SLD) x 100 where nadir represents the smallest SLD prior to the current post-baseline visit.

Note the nadir should only be identified from assessments where all the identified target lesions have a LD measurement. Furthermore, the nadir may (or may not) change at every visit where tumor assessment occurs.

QMD Ref: CCI	Governing QMD: CCI
Confidentiality Statement	
CCI	

CCI		Sponsor: Theseus Pharmaceuticals, Inc.	
CCI		Protocol Number: THE630-21-101	
STATISTICAL ANALYSIS PLAN. PHASE 2-3-4			

Percentages should be rounded to 1 decimal place prior to assigning target lesion response. For example, 19.84% should be rounded to 19.8%.

Assigning Target lesion response for a given visit

The target lesion response will be either CR, PR, SD or PD based on what criteria is met. If the patient’s SLD at a given visit meets the criteria of both PR and PD (based on percent change from baseline and percent change from nadir respectively) then the target lesion response is PD.

If the current tumor assessment has at least one missing target lesion LD measurement (e.g., MTLFLG=1) then assign the target lesion response to PD if the criteria for PD (target lesion) is met based on percent change from nadir. This is the only situation where it can be shown that the contribution of the missing lesion measurement would not change the assigned response. Otherwise, assign the target lesion response to NE.

10.2 Overall Visit Response

Overall visit response will be derived based on

- target lesion response (derived, [10.1](#)),
- nontarget lesion response -(based on [investigator reported] non-target lesion response on the eCRF Modified RECIST v1.1 Response page, RSP01.RSPNTR)
- presence of new lesions (based [investigator reported] “Any new lesions present?” (yes/no) CRF page Modified RECIST v1.1 response page, RSP01.RSNLYN).

The following table will be used:

Target Lesion	Nontarget Lesion	New Lesion (presence)	Overall Response
CR	CR	No	CR
CR	Non-CR/non-PD	No	PR
CR	NE	No	PR
PR	Non-PD (e.g. CR, Non-CR/non-PD) or NE	No	PR
SD	Non-PD (e.g. CR, Non-CR/non-PD) or NE	No	SD

QMD Ref: CCI	Governing QMD: CCI
Confidentiality Statement	
CCI	

CCI		Sponsor: Theseus Pharmaceuticals, Inc.	
CCI		Protocol Number: THE630-21-101	
STATISTICAL ANALYSIS PLAN. PHASE 2-3-4			

Not all evaluated (NE)	Non-PD (e.g., CR, Non-CR/non-PR) or NE	No	NE
PD	Any	Yes or No	PD
Any	PD	Yes or No	PD
Any	Any	Yes	PD

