## **12. APPENDICES**

## 12.1 Appendix 1: Modifications to Response Evaluation Criteria in Solid Tumors version 1.1 (RECIST 1.1), for Patients with GIST

This study will utilize response criteria adapted from RECIST 1.1 ([Eisenhauer, 2009](#)) with modification for patients with GIST, as described by Demetri and colleagues ([Demetri, 2013](#)).

The modifications to RECIST version 1.1 criteria for patients with GIST include:

1. No lymph nodes to be chosen as target lesions. Enlarged lymph nodes are to be followed up as non-target lesions
2. No bone lesions to be chosen as target lesions
3. Fluorodeoxyglucose positron emission tomography (18FDG-PET) is not acceptable for radiological assessment
4. A progressively growing new tumor nodule within a pre-existing tumor mass must meet the following criteria in order to be regarded as unequivocal evidence of progressive disease according to the aforementioned GIST-specific modifications to RECIST 1.1:
  - a. The lesion must be  $\geq 2$  cm in size and definitely be a new active GIST lesion (e.g., enhanced with contrast or other criteria to rule out artifact); or
  - b. The lesion must be expanding on at least 2 sequential imaging studies.

Source: [Demetri, 2013](#).

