### New Lesions

- Should be unequivocal and not attributable to differences in scanning technique or findings that may not be a tumor (does not have to meet criteria to be “measurable”)
- If a new lesion is equivocal, continue to next time point. If confirmed at that time, PD is assessed at the date when the lesion was first seen.
- Lesions identified in anatomic locations not scanned at baseline are considered new
- New lesions on ultrasound should be confirmed on CT or MRI

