4.2.14.2 Confirmed Objective Response Rate (ORR)

Confirmed ORR is defined as the proportion of the patients who were confirmed to have achieved CR or PR per modified RECIST version 1.1 for patients with GIST (confirmed ≥ 4 weeks after initial response with a subsequent scan) after initiation of study drug. Patients with no measurable disease at baseline or no evaluable post-baseline response assessment (e.g., RECIST) will be considered non-responders.

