10.3 BOR-confirmation of CR and PR required

BOR is calculated based on the overall visit responses obtained up until objective disease progression (i.e., RECIST response = PD). In the absence of objective disease progression, the BOR is determined using visit responses up until the last evaluable overall visit response.

CR : Overall visit response of CR confirmed at least 4 weeks later by another overall visit response of CR

PR : Overall visit response of PR confirmed at least 4 weeks later by another overall visit response of at least PR (i.e., CR/PR)

SD (≥ 6 weeks): Stable disease recorded at least 6 weeks after the date of first dose (with no prior evidence of progression)

PD: Progression in the absence of CR/PR or SD

NE: Not evaluable.

Overall response first time point	Overall response subsequent time point	Best overall response
CR	CR	CR (if subsequent time point ≥ 4 weeks after first time point)
CR	PR	SD, PD or PR ^a
CR	SD	SD-provided minimum criteria for SD duration are met. Otherwise, PD
CR	PD	SD-provided minimum criteria for SD duration are met. Otherwise, PD
CR	NE	SD-provided minimum criteria for SD duration are met. Otherwise, NE

QMD Ref: CCI	Governing QMD: CCI
Confidentiality Statement	
CCI	

CCI		Sponsor: Theseus Pharmaceuticals, Inc.	
CCI		Protocol Number: THE630-21-101	
STATISTICAL ANALYSIS PLAN. PHASE 2-3-4			

PR	CR	PR
PR	PR	PR (if subsequent time point \geq 4 weeks after first time point)
PR	SD	SD -provided minimum criteria for SD duration are met. Otherwise, PD
PR	PD	SD-provided minimum criteria for SD duration are met. Otherwise, PD
PR	NE	SD-provided minimum criteria for SD duration are met. Otherwise, NE
NE	NE	NE

^aIf a CR is truly met at first time point, then any disease seen at a subsequent time point, even disease meeting PR criteria relative to baseline, makes the disease PD at that point (since disease must have reappeared after CR). Best response would depend on whether minimum duration for SD was met.

Other considerations

There may be cases where a patient has one or more visits that are not evaluable (NE). These visits may fall in between evaluable visits. This should be taken into account. Thus, subsequent timepoint/visit does not literally mean next time point when NE visit may be involved.

[figure not shown]

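### The SAP's programmed visit response has no step for back-dating PD to an equivocal new lesion that is later confirmed, so the protocol rule holds only if the site amends the earlier entry

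*SAP*

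**What the plan says.** **Protocol, Appendix 1, New Lesions.** The rule spans two visits. First: "If a new lesion is equivocal, continue to next time point". Then: "If confirmed at that time, PD is assessed at the date when the lesion was first seen". An equivocal lesion leaves the first scan open, and confirmation makes that first scan the date of PD.

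**SAP, section 10 (Appendix 1: RECIST).** The investigator determines an overall response at each visit, but the analysis does not use it: "For analysis purposes, overall visit response will be derived via programming based on" the derived target-lesion response, the collected non-target response, and "presence of new lesions (as collected").

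**SAP, section 10.2.** The new-lesion input is "presence of new lesions (based [investigator reported" answer to a yes/no question on the response page of the eCRF). The table that follows maps that visit's three inputs to that visit's response. Nothing in it resets an earlier visit.

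**SAP, section 10.3.** "BOR is calculated based on the overall visit responses obtained up until objective disease progression". Confirmed ORR and DCR follow from BOR. CBR (section 4.2.14.3) depends on whether PD was met by the 16-week assessment.

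SAP section 7 describes the analyses as generally consistent with the protocol and does not list this difference.

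**The concern.** At the scan where a lesion is only equivocal, No is a natural entry for whether new lesions are present. The program then returns SD or PR for that visit. When the next scan confirms the lesion the entry becomes Yes, and PD is placed at that later scan. The protocol places it at the earlier one. An investigator who back-dates PD only in the overall response field has no effect on the analysis, because that field is overridden.

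The SAP does write out other rules that span visits: reappearance after CR, the nadir, confirmation of PR, and a not-evaluable scan between two PRs. The absence of this one looks like an oversight.

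At stake are BOR, confirmed ORR, DCR and CBR. BOR is the best response before PD, so adding a non-PD visit ahead of PD can leave the result unchanged or improve it, but cannot worsen it. Any error therefore favours the drug.

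**Working it through.** **Inputs**
- Scans on Day 28 ± 3 of even-numbered cycles through Cycle 12 (Protocol 7.2.1), so nominally days 56, 112 and 168 (weeks 8, 16, 24).
- SD counts from 6 weeks, i.e. 42 days, after first dose (SAP 4.2.14.1 and 4.2.14.4).
- CBR needs at least 109 days (SAP 4.2.14.3).
- ORR requires responses to be "confirmed ≥ 4 weeks after initial response with a subsequent scan" (SAP 4.2.14.2).
- 32 patients enrolled, no Phase 2 (SAP section 1).

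**The plan's own figure.** 4 cycles × 28 days − 3-day window = 109 days, which matches the CBR threshold. Two further checks: the earliest scheduled first scan is day 56 − 3 = 53, beyond 42, so SD there always qualifies; and nominal scans 56 days apart satisfy the 4-week confirmation.

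**Comparison.** Suppose a new lesion is equivocal at scan *k* and confirmed at scan *k*+1. Column A leaves the entry at scan *k* as No, so PD falls at *k*+1. Column B follows the protocol, with PD at *k*. Each cell gives BOR, then ORR/DCR/CBR (1 = success).

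| Equivocal at | Target response up to that scan | A: entry left No | B: PD back-dated | Rate that differs |
|---|---|---|---|---|
| Week 8 | SD | SD, 0/1/0 | PD, 0/0/0 | DCR |
| Week 8 | PR | SD, 0/1/0 | PD, 0/0/0 | DCR |
| Week 16 | SD, SD | SD, 0/1/1 | SD, 0/1/0 | CBR |
| Week 16 | SD, PR | SD, 0/1/1 | SD, 0/1/0 | CBR |
| Week 16 | PR, PR | PR, 1/1/1 | SD, 0/1/0 | ORR and CBR |
| Week 24 | SD, SD, SD | SD, 0/1/1 | SD, 0/1/1 | none |
| Week 24 | SD, SD, PR | SD, 0/1/1 | SD, 0/1/1 | none |
| Week 24 | SD, PR, PR | PR, 1/1/1 | SD, 0/1/1 | ORR |
| Week 24 | PR, PR, PR | PR, 1/1/1 | PR, 1/1/1 | none |

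To read one row: with PR at week 8, and PR plus an equivocal lesion at week 16 confirmed at week 24, column A sees PR, PR, PD and counts a confirmed responder. Column B sees PR, PD. The PR is unconfirmed and SAP 10.3 gives SD.

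**Pattern.** DCR differs when the first on-study scan is the equivocal one, CBR when the week-16 scan is, and ORR when the scan that first confirms a PR is. On this schedule a week-8 equivocal lesion never changes ORR or CBR, and one at week 16 or later never changes DCR if week 8 was SD or PR. If the site amends the earlier entry to Yes, column A becomes column B.

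**Size.** One reclassified patient moves an overall rate by 1/32 = 3.1 points. For illustration only, with exact 95% intervals:
- 3/32 = 9.4% (2.0–25.0) becomes 2/32 = 6.25% (0.8–20.8).
- 17/32 = 53.1% (34.7–70.9) becomes 16/32 = 50.0% (31.9–68.1).

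**The case against.** The strongest reply is that the new-lesion entry belongs to the investigator, who assesses under modified RECIST and can correct the eCRF (Protocol 10.7.1). If the earlier entry is amended after confirmation, the SAP table returns the protocol's answer. Protocol 10.7.1 also refers to separate eCRF completion guidelines, which are not part of these documents and might give that instruction. This stands, and it rules out one tempting inference: that back-dating is lost outright. It is unsecured. Nor does the correction process close the gap, since it is driven by disagreement between source and eCRF. A source note of an equivocal lesion need not conflict with a No.

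Two other stronger readings are tempting.
- *All efficacy results are affected.* The table shows otherwise, and the waterfall plot uses target-lesion diameters only. The SAP revision history drops PFS, OS and the DOR displays, so a later PD date as such has little left to act on.
- *GIST criterion 4b makes the problem common.* A nodule inside an existing mass that does not meet the size criterion counts as PD only if "The lesion must be expanding on at least 2 sequential imaging studies", so a reader might extend back-dating to it. The protocol does not. The back-dating sentence concerns equivocal lesions under New Lesions, while the 4b criterion is repeated under Nontarget Lesion Response with no dating rule.

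It is also fair that the trial stopped in Phase 1, efficacy is secondary, no cohort comparison is planned, and one patient's shift sits well inside the exact intervals. That limits the consequence. It does not reconcile the two documents.

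**Conclusion.** The point holds in a limited form. The protocol states a dating rule that the SAP's program does not implement, and the program overrides the investigator response that might have carried it. Only new lesions that are first equivocal and then confirmed matter; unequivocal ones are PD at the same visit under both documents. When the earlier entry stays No, DCR, CBR or confirmed ORR may be counted too favourably according to which scan was equivocal. Two of them move together when the week-16 scan is also the first to confirm a PR, and in other patterns none moves.

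The number of such patients is not in the documents, so no total bias can be given: only 3.1 points per reclassified patient overall, always in the drug's favour. This assumes that all 32 enrolled patients received a dose and so form the Full Analysis Set, and that scans fall on schedule. It should be corrected because the error runs one way and the remedy is small.

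**What to change.** Add to SAP 10.2: when a new lesion first seen as equivocal is confirmed at the next assessment, the overall visit response is PD from the visit at which it was first seen. Apply this before BOR, ORR, DCR and CBR are derived. Limit it to new lesions as the protocol does, without extending it to criterion 4b nodules.

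Before database lock:
- For each patient whose first Yes for new lesions follows a non-PD scan, query the site for the date the lesion was first seen. The SAP names no field that holds this date.
- Tabulate derived against investigator overall response by visit, so that any remaining disagreement is visible.

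The cost is one derivation rule and a short query list among 32 patients. ORR, DCR or CBR may fall slightly.
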